## 8.6 Interim Analysis

No interim analysis is planned.

## 8.7 Sample Size and Randomization

The sample size for this study is based on an infection rate in the placebo group of 10%. A 2:1 randomization of 225 subjects would have a power of 80.8% to detect a difference of 9% between groups at alpha = 0.05 assuming 1% of individuals in the treatment group was confirmed to be infected with SARS-CoV-2. [Table 8.7-1](#) below provides a range of treatment rates that could be detected with at least 80% power using this sample size.

**Table 8.7-1 Range of treatment rates detectable with at least 80% power**

Treated Infection Rate (N=150)	Placebo Infection Rate (N= 75)	Difference Treated - Placebo	Actual Power
0	7.3%	-7.3%	80.3%
1%	10%	-9%	80.8%
2.5%	13.5%	-11%	80.3%
5%	18.1%	-13.1%	80.4%
7.5%	22.1%	-14.6%	80.3%
10%	25.7%	-15.7%	80.0%

## 8.8 Missing Values

If a subject is lost to follow-up, or for some reason fails to provide an assessment of the primary endpoint, the subject will be considered a treatment failure per the ITT population.

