### **8.1 Data Sets to be Analyzed**

Any participant who is randomized to a treatment allocation will be considered part of the intention-to-treat (ITT) population. The ITT population will be used for the summary of all demographic and baseline characteristics and for analysis of the primary outcome. Subjects lost to follow-up, requiring rescue therapy, those who discontinue study prior to completion of the primary treatment

end point (Week 4) and those who test positive for SARS-CoV-2 infection at Weeks 2 or 4 will be considered as treatment failures. Separate analysis will examine treatment failures in the period between the cessation of study treatment (Week 4) and the end of study (Week 6). All deaths will be considered as treatment failures. All subjects will be grouped in analyses and summaries based on their randomization allocation. The following analysis populations will be defined from the ITT population:

- The safety analysis set includes all randomized participants and is synonymous with the ITT set except that patients will be grouped based on treatment actually received.
- Per-protocol (PP) analysis set includes all participants who complete the trial and who receive ≥90% Study Treatments through to either diagnosis of SARS-CoV-2 infection (study end point) or to end of study for those without a SARS-CoV-2 diagnosis, based on subject completed accountability logs, and have no significant protocol violations. Participants in this sample will be grouped to treatment arms they actually received. This set will be used as a sensitivity analysis to summarize the primary and secondary efficacy outcomes.

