##### **6.3. Per-protocol (PP) Population**

The PP Population will include all subjects who complete the trial and who receive  $\geq 90\%$  of the study treatments through to either diagnosis of SARS-CoV-2 infection (study end point) or to end of study (4 weeks), based on subject's completed doses on the treatment diary form, and who have no significant protocol deviations.

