## **APPENDIX C: TABLE LAYOUTS**

Table 14.1.1.1  
Subject Disposition  
(All Subjects)

Study Site Subject Status	GLS-1200	Placebo	Overall
Overall			
Screened			xx
Screen Failures			xx
ITT Population [1]	xx	xx	xx
Safety Population [2]	x (xx.x%)	x (xx.x%)	x (xx.x%)
PP Population [3]	x (xx.x%)	x (xx.x%)	x (xx.x%)
Completed the study [4]	x (xx.x%)	x (xx.x%)	x (xx.x%)
Discontinued the study	x (xx.x%)	x (xx.x%)	x (xx.x%)
Reason for discontinuation			
<Reason #1>	x (xx.x%)	x (xx.x%)	x (xx.x%)
<Reason #2>	x (xx.x%)	x (xx.x%)	x (xx.x%)
<Reason #3>	x (xx.x%)	x (xx.x%)	x (xx.x%)
Site 101			
.			
.			
Site 108			
.			
.			

Percentages are based on the ITT Population.

[1] The Intent-to-treat (ITT) Population includes all randomized to treatment allocation.

[2] The Safety Population includes all subjects who received at least one dose of study treatment.

[3] The Per-protocol (PP) Population includes all subjects who completed the trial, received  $\geq 90\%$  of the study treatments, and have no significant protocol deviations. Trial completion is defined as either completing Week 4 or meeting the study endpoint of PCR confirmed SARS-CoV-2 infection.

[4] Study completion is defined as completing all visits regardless of drug compliance.

Reference: Listing 16.2.1

Source: \\xx\\xx\\xx\\xx\\xx\\xxxx\\xxxxxxxxxxxx\\xxxx\\xxxx.sas      date      time

**Programming note:** Sort discontinuation reasons by descending overall frequency. List all reasons per CRF page.

Table 14.1.1.2  
Reason for Screen Failure  
(All Screen Failure Subjects)

Study Site	Reason	Overall (xx)
Overall		
<Reason #1>		x (xx.x%)
<Reason #2>		x (xx.x%)
<Reason #3>		x (xx.x%)
Site 101		
<Reason #1>		x (xx.x%)
<Reason #2>		x (xx.x%)
<Reason #3>		x (xx.x%)
Site 108		
<Reason #1>		x (xx.x%)
<Reason #2>		x (xx.x%)
<Reason #3>		x (xx.x%)

Reference: Listing 16.2.3 and Listing 16.2.1

Source: \\xx\\xxx\\xxx\\xxx\\xxxxxx\\xxxxxxxxxxxx\\xxxx\\xxxxx.sas      date      time

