>80%	x (xx.x%)	x (xx.x%)

Site 101

.

Site 108

.

[1] Duration of exposure is defined as the date of last dose minus the date of first dose + 1.

[2] Treatment compliance is defined as the total number of doses taken divided by the total number of planned doses times 100.

Reference: Listing 16.2.5.1 and Listing 16.2.1

Table 14.2.1.1  
Incidence of SARS-CoV-2 Infection by Visit  
(ITT Population)

	GLS-1200 (N=XX)	Placebo (N=XX)	p-value [1]
Treatment Success [2]	x (xx.x%)	x (xx.x%)	
Treatment Failure [3]	x (xx.x%)	x (xx.x%)	
Lost to follow-up	x (xx.x%)	x (xx.x%)	
Required rescue therapy	x (xx.x%)	x (xx.x%)	
Discontinued study prior to completion of Week 4	x (xx.x%)	x (xx.x%)	
Tested positive for SARS-CoV-2 infection at any time up to Week 4	x (xx.x%)	x (xx.x%)	
Had missing PCR result at any visit up to Week 4	x (xx.x%)	x (xx.x%)	
Died	x (xx.x%)	x (xx.x%)	
Week 0 PCR Result			
n	x	x	
Negative	x (xx.x%)	x (xx.x%)	
Positive	x (xx.x%)	x (xx.x%)	
Missing	x (xx.x%)	x (xx.x%)	
Week 2 PCR Result			
n	x	x	
Negative	x (xx.x%)	x (xx.x%)	
Positive	x (xx.x%)	x (xx.x%)	
Missing	x (xx.x%)	x (xx.x%)	
...			

[1] The p-value is calculated using a Fisher's exact test.

[2] Subjects who test negative for SARS-CoV-2 infection at Weeks 2 and 4 are considered treatment successes.

[3] Subjects who met any of the reasons listed are considered treatment failures. Subjects who fail treatment for multiple reasons are counted once for each reason.

Reference: Listing 16.2.6.1

Source: \\xx\\xxx\\xxx\\xxx\\xxxxxx\\xxxxxxxxxxxx\\xxxx\\xxxxx.sas      date      time

**Programming note: Continue for remaining visits. Repeat for Table 14.2.1.2 Incidence of SARS-CoV-2 Infection (PP Population).**

Table 14.2.2  
Incidence of Individual Symptoms and Average Number of Days with Symptoms by Visit Interval  
(ITT Population)

Symptom	GLS-1200 (N=XX)	Placebo (N=XX)
Subjects who reported Body Aches at least once from Day 1 to Week 2	x (xx.x%)	x (xx.x%)
Subjects who reported Body Aches at least once from Week 2 to Week 4	x (xx.x%)	x (xx.x%)
Subjects who reported Body Aches at least once from Week 4 to Week 6	x (xx.x%)	x (xx.x%)
Subjects who reported Body Aches at least once during the overall treatment phase [1]	x (xx.x%)	x (xx.x%)
Number of days subjects reported Body Aches from Day 1 to Week 2		
n	x	x
Mean (SD)	xx.x (xx.xx)	xx.x (xx.xx)
Median	xx.x	xx.x
Min, Max	xx, xx	xx, xx
Number of days subjects reported Body Aches from Week 2 to Week 4		
n	x	x
Mean (SD)	xx.x (xx.xx)	xx.x (xx.xx)

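### The SAP table shell extends missing-counts-as-failure to the per-protocol set without saying so, so the PP test partly compares missed swabs and not infection

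*Protocol*

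**What the plan says.** **Missing-data rule.** Protocol 8.8 covers participants who are lost or otherwise give no assessment of the primary endpoint: "the subject will be considered a treatment failure per the ITT population". No other population is named there, and neither document states a missing-data rule for PP.

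**Role and membership of PP.** Protocol 8.1 says of the PP set: "This set will be used as a sensitivity analysis to summarize the primary and secondary efficacy outcomes". Members are those "who receive ≥90% Study Treatments through to either diagnosis of SARS-CoV-2 infection" or to the end of study. SAP 6.3 begins "The PP Population will include all subjects who complete the trial and who receive" at least 90% of treatments, and adds those "who have no significant protocol deviations". Footnote [3] of SAP Table 14.1.1.1 explains completion: "Trial completion is defined as either completing Week 4 or meeting the study endpoint of PCR confirmed SARS-CoV-2 infection". None of these conditions asks for a full set of swab results, and neither document defines a significant deviation.

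**Endpoint and test.** SAP 8.1 defines success as negative results at Weeks 2 and 4. Its failure list covers loss to follow-up, rescue therapy, discontinuation before Week 4, a positive test and death. Missing PCR is not on it. SAP 8.2 compares failures and successes with Fisher's exact test in both ITT and PP.

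**Table shell.** The failure reasons in Table 14.2.1.1 include one more: "Had missing PCR result at any visit up to Week 4". Footnote [3] of that table makes anyone with a listed reason a failure. The programming note then says: "Repeat for Table 14.2.1.2 Incidence of SARS-CoV-2 Infection (PP Population)". It changes no rows.

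**The concern.** A PP analysis of a prevention endpoint is normally expected to show the effect on infection among people who took the product and were followed. In this PP set, loss to follow-up and discontinuation before Week 4 are removed by definition, so the missing-PCR row becomes the main way in which people with no observed infection enter the analysis as failures. Someone with at least 90% of doses, an absent or unreadable Week 2 swab and a negative Week 4 swab cannot be a success, because success needs both negatives. The shell makes that person a failure of prevention.

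The rule sits only in a layout. A reader of the SAP body would not know that it applies to PP, or that it exists at all. With very few infections expected on GLS-1200, a handful of missed swabs can outnumber the real events and blunt the one planned sensitivity analysis of the primary endpoint.

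**Working it through.** **1. Trace one participant.** Take at least 90% of doses, Week 4 completed, no significant deviation recorded, Week 2 PCR missing and Week 4 PCR negative.
- PP membership (SAP 6.3; Table 14.1.1.1 footnote [3]): yes.
- Success (SAP 8.1): no, because the Week 2 negative is absent.
- Failure under the SAP 8.1 text: no listed reason applies, so the person is unclassified.
- Failure under the Table 14.2.1.1 shell, repeated for PP: yes.

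**2. Reproduce the plan's power.** Inputs from Protocol 8.7: 150 v 75, infection 1% v 10%, alpha 0.05, stated power 80.8%. SAP 8.2 gives Fisher's exact test. Exact binomial enumeration with the two-sided p-value taken as twice the smaller tail gives 80.9%, which matches. Ordinary (probability-ordered) two-sided Fisher gives 87.6%. Both conventions are shown below.

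**3. Add missing swabs.** Let m be the share of uninfected PP participants with a missing PCR, equal in both arms. The documents give no value, so m = 2% and 5% are assumptions. A PP set of 120/60 (80% of those randomized) is also an assumption.

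Failure rate = p + (1 − p)m
- m = 2%: GLS-1200 0.01 + 0.99 × 0.02 = 2.98%; placebo 0.10 + 0.90 × 0.02 = 11.8%; ratio 0.25
- m = 5%: GLS-1200 0.01 + 0.99 × 0.05 = 5.95%; placebo 0.10 + 0.90 × 0.05 = 14.5%; ratio 0.41
- m = 0: ratio 0.01 / 0.10 = 0.10

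| PP size | Fisher convention | m = 0 | m = 2% | m = 5% |
|---|---|---|---|---|
| 120/60 | doubled tail | 68.7% | 50.1% | 35.4% |
| 120/60 | ordinary two-sided | 80.1% | 59.2% | 41.7% |
| 150/75 | doubled tail | 80.9% | 61.4% | 45.0% |
| 150/75 | ordinary two-sided | 87.6% | 69.2% | 51.1% |

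At 120/60 and m = 5%, the expected GLS-1200 counts are 120 × 0.01 = 1.2 infections against 120 × 0.99 × 0.05 = 5.9 missed swabs counted as failures.

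**4. Worked example (ordinary two-sided Fisher).** Infections of 1/120 v 6/60 give p = 0.006. Adding about 2% missing as failures (3/120 v 7/60) gives p = 0.017. Adding 5% (7/120 v 9/60) gives p = 0.053.

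**5. Leave them out instead.** Dropping 5% from each arm gives 114/57. Doubled-tail power is then 65.6%, against 68.7% with no missing swabs: a loss of about 3 points.

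**6. Bias from leaving them out.** If positives are kept but 5% of non-positives are dropped, the rates become 0.10 / (0.10 + 0.90 × 0.95) = 10.5% and 0.01 / (0.01 + 0.99 × 0.95) = 1.05%. Both rise slightly.

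**The case against.** **The SAP breaches the protocol.** A reader might infer this, but the documents do not support it. Protocol 8.8 names ITT without excluding other sets, and Protocol section 8 lets the SAP modify the planned analysis. This is an undeclared extension, not a contradiction.

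**The PP results cannot separate infections from imputed failures.** This too is tempting and does not hold. SAP 8.2 asks for positives and negatives by arm at each visit, and the shell has separate rows for a positive test up to Week 4 and for a missing PCR. What is absent is a test on the observed positives.

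**A missed swab may be a significant deviation.** If it were ruled so, the participant would leave PP and the problem would go with them. Protocol 4.4 sends failures to adhere to the Medical Monitor and the site investigator, and Listing 16.2.2 grades deviations as major or minor. That is a fair condition on the point. But neither document says how a missed swab is graded, and an unreadable swab is not obviously a failure to adhere.

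**The size is assumed.** This stands. The missing-swab rate and the PP size are not in the documents, the power level depends on the Fisher convention, and at about 2% missing the worked example stays below 0.05. PP is also a supporting analysis, so power is only a gauge of how far the comparison is diluted.

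**Conclusion.** The point holds in a limited form. The table shell alone brings missing-counts-as-failure into PP, and the SAP body neither states nor justifies it. Unless missed swabs are ruled significant deviations, adherent completers with one missing result are tested as failures, and no planned test compares observed infection in their place.

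Under equal missingness of 2% to 5%, infection of 1% v 10% and a PP set of 120/60, power falls by 19 to 33 points with doubled-tail Fisher, or by 21 to 38 points with ordinary two-sided Fisher. The direction does not depend on the convention; the amount depends on a missing-swab rate that is not stated. The primary ITT analysis is not affected.

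**What to change.** - **SAP 8.1/8.2:** define the PP comparison as PCR-confirmed infection up to Week 4 on observed results, with missing PCR not counted as failure. In the same edit, say whether missing PCR is a failure in ITT, so that the SAP 8.1 list and the Table 14.2.1.1 shell agree.
- **Table 14.2.1.2:** give it its own shell without the missing-PCR failure row.
- **SAP 6.3:** state how a missed or unreadable Week 2 or Week 4 swab is handled, including whether it is a significant deviation, and report the number of such participants by arm.
- **Check:** excluding only non-positives with a missing swab slightly raises both rates, so repeat the comparison with every PP participant who has no observed positive counted as not infected.

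The cost is a few sentences, one more shell and a small loss of PP power (about 3 points at 5% missing, doubled-tail Fisher). The primary ITT analysis is unchanged.

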# 9. DATA COLLECTION, MONITORING, AND AE REPORTING

## 9.1 Confidentiality

Information about study participants will be kept confidential to the best of the study site's ability.

In the event that a participant revokes authorization to collect or use personal health information (PHI), the sponsor retains the ability to use all information collected prior to the revocation of participant authorization. For participants that have revoked authorization to collect or use PHI, attempts should be made to obtain permission to collect at least vital status (i.e., that the participant is alive) at the end of their scheduled study period.

## 9.2 Source Documents

Source data is all information, original records or clinical findings, observations, or other activities in a clinical trial necessary for the reconstruction and evaluation of the trial. Source data are contained in original source documents. Examples of these original documents, and data records include (as applicable): hospital records, clinical and office charts, laboratory notes, memoranda,

participant's diaries or evaluation checklists, pharmacy dispensing records, recorded data from automated instruments, copies or transcriptions certified after verification as being accurate and complete, microfiches, photographic negatives, microfilm or magnetic media, x-rays, participant files, pharmacy records, laboratory records, medical records (including electronic records) relative to the clinical trial.

### **9.3 Data Collection**

Data will be collected using Electronic Data Capture (EDC). Participants will be identified by PID#. Initial data collection may utilize a paper form of the EDC. Any such records will be maintained as source data.

### **9.4 Record Retention**

It is the Investigator's responsibility to retain study essential documents as per country regulations: in the US for at least 2 years after the last approval of a marketing application in their country and until there are no pending or contemplated marketing applications in their country or at least 2 years have elapsed since the formal discontinuation of clinical development of the investigational product. The sponsor will inform the investigator/institution as to when these documents are no longer needed to be retained.

### **9.5 Safety and Quality Monitoring and Record Availability**

#### Monitoring

Monitoring of the clinical trial will be performed by experienced monitors, who will report to the Sponsor as outlined in the Monitoring Plan.

#### Record availability and auditing

The investigator will make study documents (e.g., ICFs, drug accountability forms) and pertinent hospital or clinic records readily available for inspection by the local IRB, the site monitors, regulatory agencies, GeneOne Life Science, Inc. or its designee for confirmation of the study data.

Participation as an investigator in this study implies acceptance of potential inspection by regulatory authorities and applicable compliance and quality assurance offices.

### **9.6 Adverse event (AE) Reporting**

To assure the safety of the participants, information about all AEs, whether volunteered by the participant, discovered by investigator or study staff questioning, or detected through physical examination, laboratory test or other means, will be collected and recorded in the participant's source documents and followed as appropriate.

A summary of the study's overall progress will be forwarded to regulatory agencies according to the local requirements.

#### **9.6.1 Study Reporting Period of Adverse Events**

Solicited and unsolicited AEs will be collected throughout the study and recorded.

#### **9.6.2 Study Reporting Period for Serious Adverse Events**

SAEs occurring from the time of consent through to the end of the study are to be reported without regard to causality. SAE's should be reported to GeneOne Life Science within 24 hours of discovery. Investigators should also report SAEs to their local IRB/REC as required.

---

Expedited reporting of SAEs will be determined by GeneOne Life Science using reference safety information specified in the Investigator's Brochure. An event may qualify for expedited reporting to regulatory authorities if it is an SAE, unexpected per reference safety information and considered related following the guidelines in Section 7.1.4 (Suspected Unexpected Serious Adverse Reaction, SUSAR) in line with relevant legislation. All investigators will receive a safety letter notifying them of relevant SUSAR reports. The Investigator should notify the Ethics Committee as soon as is practical, of serious events in writing where this is required by local regulatory authorities, and in accordance with the local institutional policy.

At any time after completion of the SAE reporting period, if an Investigator becomes aware of an SAE that is suspected by the Investigator to be related to the study drug, the event will be reported to the Sponsor or its designee.

If the Investigator becomes aware of an SAE after the last scheduled follow-up contact, and considers the event related to prior Study Treatment, the Investigator will report it to GeneOne Life Science.

### **9.6.3 Notification of Serious Adverse Events**

In accordance with local regulations, the Sponsor shall notify the appropriate regulatory authorities, and all participating investigators in a written safety report of any adverse experience associated with the use of the product that is both serious and unexpected (e.g., FDA Form 3500A in the US). Reports of SAEs shall be made as soon as possible and in no event later than 15 calendar days after the Sponsor's initial receipt of the information. Written notification may be submitted on the form described above or equivalent or in a narrative format and shall bear prominent identification of its contents. Each written notification to regulatory agencies shall be transmitted to the division that has responsibility for review. In each written safety report, the Sponsor shall identify all safety reports previously filed concerning a similar adverse experience, and shall analyze the significance of the adverse experience in light of the previous, similar reports. The Sponsor shall also notify the relevant regulatory authorities by telephone, facsimile, or email transmission of all deaths and any unexpected fatal or life-threatening experience, regardless of causality, as soon as possible but in no event later than 7 calendar days after the Sponsor's initial receipt of the information. Each telephone call or facsimile transmission to regulatory agencies shall be transmitted to the division that has responsibility for review.

Follow up information to a safety report shall be submitted as soon as the relevant information is available. If the results of a Sponsor's event investigation show that an adverse drug experience not initially determined to be reportable is, in fact, reportable, the Sponsor shall report such experience in a written safety report as soon as possible, but in no event later than 15 calendar days after the determination is made. Results of investigations of other safety information shall be submitted, as appropriate, in an information amendment or annual report. In the event of death, if an autopsy is performed, a copy of the report, redacted for PHI but labeled with the PID#, should be sent to GeneOne Life Science, Inc.

### **9.7 Study Discontinuation**

GeneOne Life Science reserves the right to discontinue the study for safety or administrative reasons, including lack of enrollment, at any time. Investigational product must be returned to GeneOne, unless instructed otherwise. Document retention will follow local regulation.

## **10. PUBLICATION OF RESEARCH FINDINGS**

Publication of the results of this trial will be allowed. Any proposed presentation, abstract and/or manuscript must be made available to GeneOne at least 60 days prior to submission. GeneOne shall have fifteen (15) days for review. If GeneOne considers that material would reveal protectable intellectual property, GeneOne may request a delay in submission for a maximum of three (3) months from the date of receipt in order for patent application(s) to be filed with the United States Patent and Trademark Office and/or foreign patent office(s).

